SPIDER Study Protocol

Study Title

SPIDER – *Spinal Dural Arteriovenous Fistula International Data and Outcomes Registry*

Principal Investigator

[name], FAANS, FACS, FAHA

The [name] Distinguished Professor of Neurological Surgery and Radiology

Division Chief of Neurovascular Surgery & Endovascular Neurosurgery

Thomas Jefferson University Hospital

Study Coordinator / Contact

[name] [name]

Research Fellow, Department of Neurosurgery

Thomas Jefferson University Hospital

Study Version and Date

Version 1.0 – 20 December 2025

Background and Rationale

Spinal dural arteriovenous fistulas (SDAVFs, type I spinal vascular malformations) are the most common spinal vascular malformation but remain frequently underdiagnosed due to their insidious onset and nonspecific clinical presentation. Delayed diagnosis is common and often results in progressive, and sometimes irreversible, myelopathy. Despite advances in imaging and treatment, there remains significant variability in diagnostic timelines, treatment strategies (endovascular, surgical, or combined), and reported outcomes across institutions.

Existing literature is largely limited to single-center retrospective series or small cohorts, often underpowered to evaluate predictors of outcome, recurrence, and the impact of diagnostic delay. Furthermore, direct comparisons between treatment modalities and long-term functional outcomes using standardized clinical scales are limited.

The SPIDER registry is designed to address these gaps by creating the largest international, multicenter dataset of patients with spinal dural AVFs. By pooling de-identified data from high-volume centers worldwide, this study aims to provide robust, generalizable evidence to inform clinical decision-making and optimize patient outcomes.

Study Objectives

Primary Objectives

1. To characterize the clinical, radiological, and angiographic presentation of spinal dural AVFs.
2. To compare treatment strategies (endovascular, surgical, combined, or conservative management) and their angiographic and clinical outcomes.
3. To evaluate long-term neurological and functional outcomes following treatment.
4. To assess the impact of diagnostic delay on neurological status and long-term outcomes.

Secondary Objectives

- To identify factors associated with treatment failure or recurrence.
- To evaluate complication rates associated with different treatment modalities.

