- To explore predictors of functional recovery using standardized outcome measures.

Study Design

This is an **international, multicenter, retrospective observational cohort study**.

Participating centers will contribute de-identified data on patients diagnosed with spinal dural arteriovenous fistulas who were evaluated and/or treated at their institution.

No interventions will be performed as part of this study. All data are derived from existing medical records, imaging, and procedural reports.

Study Population

Inclusion Criteria

- Patients of any age diagnosed with **spinal dural arteriovenous fistula (Type I)**.
- Diagnosis confirmed by spinal angiography, MRI findings consistent with SDAVF, and/or operative findings.
- Patients managed with endovascular treatment, open surgery, combined approaches, or conservative management.
- Both symptomatic and incidental/asymptomatic cases.

Exclusion Criteria

- Intramedullary spinal vascular malformations (e.g., glomus AVMs, juvenile AVMs).
- Perimedullary AVFs or other non-dural spinal vascular lesions.
- Cases lacking sufficient data to confirm diagnosis or treatment details.

Data Collection and Variables

Each participating center will extract data using a standardized spreadsheet with predefined categorical options to ensure consistency across sites. All data will be fully de-identified prior to submission.

Demographics and Center Information

- Country

- Study center (institution name)
- Patient study number
- Age at diagnosis
- Sex

Clinical History and Presentation

- Months from symptom onset to diagnosis
- Misdiagnoses prior to SDAVF diagnosis
- History of spinal trauma
- Incidental/asymptomatic presentation
- Presentation with rupture (spinal, intracranial, both, or none)
- Presence of myelopathy at diagnosis
- Presenting symptoms: back pain, radicular pain, sensory symptoms, motor weakness, spasticity

Functional Status at Diagnosis

- Modified Aminoff–Logue Scale (Gait)
- Modified Aminoff–Logue Scale (Bladder)
- Modified Rankin Scale (mRS)

Radiological and Angiographic Characteristics

- Laterality of fistula
- Spinal level of fistula (highest level if multilevel)
- Number of arterial feeders
- Highest and lowest arterial feeder levels (if multiple)
- Involvement of the artery of Adamkiewicz
- MRI findings (myelomalacia, cord edema, or T2 hyperintensity)

Treatment Details

- Year of treatment
- Time from diagnosis to first treatment
- Initial treatment modality:

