 - Endovascular embolization alone
 - Open surgery alone
 - Combined approaches
 - Conservative management
- Endovascular details:

- Number of embolization attempts
- Embolic agent used
- Angiographic outcome
- Intra- or postprocedural complications
- Surgical details:
 - Intraoperative visualization modality
 - Indication for visualization
 - Surgical outcome (successful or unsuccessful disconnection)
 - Intra- or postoperative complications

Recurrence and Re-treatment

- Occurrence of recurrence
- Time to recurrence
- Treatment modality for recurrence
- Angiographic outcome after re-treatment

Follow-Up and Outcomes

- Duration of follow-up
- Symptom evolution at last follow-up (pain, sensory, motor)
- Modified Aminoff–Logue Scale (Gait and Bladder) at last follow-up
- Modified Rankin Scale at last follow-up
- Overall clinical status at last follow-up (improved, unchanged, worsened)
- Death, if applicable

Notes

- Additional relevant clinical or radiological comments

Outcomes

Primary Outcomes

- Functional outcome at last follow-up as measured by mRS and Modified Aminoff–Logue scales.
- Angiographic success (complete vs partial vs unsuccessful occlusion).

Secondary Outcomes

- Rate and predictors of recurrence.
- Complication rates by treatment modality.
- Association between diagnostic delay and neurological outcome.

Statistical Analysis Plan

Descriptive statistics will be used to summarize demographic, clinical, radiological, and treatment characteristics. Continuous variables will be reported as means with standard deviations or medians with interquartile ranges, as appropriate. Categorical variables will be reported as frequencies and percentages.

Comparative analyses will be performed to evaluate outcomes across treatment modalities using appropriate statistical tests (e.g., chi-square, t-test, ANOVA, or non-parametric equivalents). Multivariable regression models may be used to identify independent predictors of outcomes and recurrence.

Missing data will be handled using appropriate statistical methods depending on the extent and pattern of missingness.

Ethical Considerations

This study involves retrospective collection of **fully de-identified data** and poses minimal risk to participants. No direct patient contact will occur, and no protected health information will be shared.

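### The comparison of non-randomised treatment groups, a primary objective, commits only to unadjusted tests; covariate adjustment is optional and not tied to treatment

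*Protocol*

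**What the plan says.** The second primary objective (Protocol, Study Objectives) reads: "To compare treatment strategies (endovascular, surgical, combined, or conservative management) and their angiographic and clinical outcomes". The Study Design section describes a retrospective observational cohort in which "All data are derived from existing medical records, imaging, and procedural reports", so treatment was whatever each centre gave in routine care.

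The two primary outcomes (Protocol, Outcomes) are "Functional outcome at last follow-up as measured by mRS and Modified Aminoff–Logue scales" and "Angiographic success (complete vs partial vs unsuccessful occlusion"). The functional outcome is the level reached at last follow-up, not the change from baseline.

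For the comparison, the Statistical Analysis Plan section says that analyses will be done to "evaluate outcomes across treatment modalities using appropriate statistical tests (e.g., chi-square, t-test, ANOVA, or non-parametric equivalents"). The next sentence adds: "Multivariable regression models may be used to identify independent predictors of outcomes and recurrence".

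The inclusion criteria admit "Both symptomatic and incidental/asymptomatic cases". Under "Functional Status at Diagnosis" the registry collects mRS and the gait and bladder scores. Elsewhere in Data Collection and Variables it collects age, months from symptom onset to diagnosis, myelopathy, MRI findings, fistula level, artery of Adamkiewicz involvement, year of treatment and centre.

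**The concern.** The crude comparison is stated as something that will be done; regression is stated as something that may be done. The regression sentence names no exposure and does not mention the treatment contrast. An analyst could follow the text to the letter and report the second primary objective from unadjusted tests alone.

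The protocol's own background gives reason to care. It says that treatment strategies and reported outcomes vary between institutions, so centre may be related to both. It also says that late diagnosis can leave lasting myelopathy, so status at diagnosis bears on status at follow-up. If severity or centre also differs between modalities, a crude difference in follow-up scores mixes that difference with any effect of treatment. The results are meant to guide treatment selection, and a larger registry makes a biased difference more likely to reach significance. Leaving adjustment open also allows the decision to be taken after the crude results are known.

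**Working it through.** The protocol states no sample size, effect size or alpha for this comparison, so there is no figure of its own to reproduce. Every input below is assumed, to show how the mechanism scales.

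**Two-group illustration, no true treatment effect**

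- Good outcome: 80% if mild at baseline, 40% if severe, whichever treatment is given.
- Severe share: 40% in group A, 60% in group B.
- Crude rate in A: 0.4 × 0.4 + 0.6 × 0.8 = 0.64.
- Crude rate in B: 0.6 × 0.4 + 0.4 × 0.8 = 0.56.
- Spurious gap: 8 percentage points. Within each severity stratum the true difference is zero.

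With n per group and a mean rate of 0.60, z = gap / √(2 × 0.6 × 0.4 / n). The two-sided 5% rejection probability is P(Z > 1.96 − z) + P(Z < −1.96 − z).

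| n per group | z, gap 8 points | rejection | z, gap 4 points | rejection |
|---|---|---|---|---|
| 150 | 1.41 | 29% | 0.71 | 11% |
| 250 | 1.83 | 45% | 0.91 | 15% |
| 500 | 2.58 | 73% | 1.29 | 25% |

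The 4-point columns arise in either of two ways:

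- Milder imbalance, severe shares 45% and 55%: 0.45 × 0.4 + 0.55 × 0.8 = 0.62 against 0.55 × 0.4 + 0.45 × 0.8 = 0.58.
- Weaker prognostic effect, good outcome 70% and 50% with shares again 40% and 60%: 0.4 × 0.5 + 0.6 × 0.7 = 0.62 against 0.6 × 0.5 + 0.4 × 0.7 = 0.58.

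In general the spurious gap is the prognostic gap times the difference in severe share. It vanishes if either is zero.

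**Simulation on a six-level ordinal scale, no true treatment effect**

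Two groups, 1,000 replicates, two-sided 5% tests. The baseline severity shift and the latent baseline-outcome correlation r are assumed. The adjusted analysis is a linear model with the baseline score as covariate.

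| n per group | shift (SD) | r | mean difference | t-test | Mann-Whitney | adjusted |
|---|---|---|---|---|---|---|
| 100 | 0.2 | 0.4 | 0.109 | 8.2% | 8.0% | 4.6% |
| 100 | 0.2 | 0.7 | 0.175 | 15.7% | 14.9% | 4.6% |
| 100 | 0.4 | 0.4 | 0.206 | 19.7% | 19.5% | 5.2% |
| 100 | 0.4 | 0.7 | 0.348 | 48.0% | 45.8% | 5.0% |
| 250 | 0.2 | 0.4 | 0.104 | 13.4% | 13.0% | 4.3% |
| 250 | 0.2 | 0.7 | 0.179 | 33.6% | 31.6% | 4.6% |
| 250 | 0.4 | 0.4 | 0.207 | 42.0% | 41.1% | 5.1% |
| 250 | 0.4 | 0.7 | 0.358 | 86.8% | 85.1% | 5.5% |

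With no shift, all three analyses rejected between 4.1% and 5.8% of the time. Two things follow. The rank test is biased almost as much as the t-test, so the non-parametric option does not remove the problem. And the t-test on an ordinal scale does no visible harm when the groups are balanced. The adjusted column is a best case, because baseline severity is the only confounder in the simulation and it is recorded.

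**The case against.** The strongest reply is that the text does not forbid adjustment. The tests are examples of appropriate methods, the next sentence allows multivariable regression for outcomes, and modality could be one of the predictors entered. Covariate lists and model forms commonly sit in a separate SAP, which may exist and is not shown. All of that is fair, and the absence of model detail is not the point. What stands is the contrast in commitment: the unadjusted comparison is promised, while adjustment is optional and has another stated purpose.

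A reader might go further in four ways that the documents do not support.

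- That severity differences will be reported as treatment effects. No imbalance between groups is documented, nor any decision to omit regression. The protocol reports variation in treatment strategies between institutions but does not say why a modality was chosen.
- That asymptomatic cases are bound to enter the comparison. The inclusion criteria set eligibility for the registry, not the analysis set, and asymptomatic presentation is a recorded variable.
- That the tests are wrong for ordinal scales. Non-parametric equivalents are allowed, chi-square is legitimate for categorical outcomes, and the simulation shows almost no extra error from the t-test itself.
- That baseline adjustment would bring a set gain in precision. The usual factor 1/(1 − r²) belongs to a linear model with a covariate unrelated to group. It does not carry over to confounded groups or to a proportional-odds model.

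**Conclusion.** The concern holds as a defect of commitment. For a primary objective in a non-randomised cohort, the only analysis promised leaves baseline severity and centre uncontrolled, although the registry collects what is needed to adjust for them. The size cannot be taken from the documents. Under the assumed inputs, a null treatment effect yields a spurious gap of 4 to 8 percentage points and a rejection rate of 11% to 73% across 150 to 500 per group, against a nominal 5%. These figures depend on the assumed prognostic gap, severity imbalance and group size; they show a risk and are not an estimate for this registry. It should be settled before the analysis planned for 2026 begins.

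**What to change.** State that the treatment comparison will be a covariate-adjusted regression with initial modality as the exposure:

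- Functional outcomes: ordinal regression of follow-up mRS, and separately of the gait and bladder scores, each adjusted for the baseline value of the same scale.
- Angiographic success: a corresponding adjusted model. The data list records an angiographic outcome under endovascular details but successful or unsuccessful disconnection under surgical details, so an outcome definition common to both groups must be stated.
- Covariates named in advance for both: age, symptom duration, myelopathy, MRI findings, fistula level, artery of Adamkiewicz involvement and year of treatment.
- Centre: accounted for in the model itself, for example as a random effect. Clustered standard errors alone would leave centre differences in the estimate.
- Asymptomatic cases: analysed separately or as a stratum.
- All four strategies in the objective kept, descriptively where a group is too small or not comparable.
- Unadjusted tests labelled descriptive.

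The cost is protocol wording and a little more analysis. The covariates are already on the collection list. Adjusted estimates may be less striking than crude ones, and confounding by unrecorded or poorly recorded factors will remain, so the report should say so.

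### The tests named for comparing modalities assume independent records and ignore center, and the entry rule lets two centers enter the same patient

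*Protocol*

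**What the plan says.** The Study Design section describes an "international, multicenter, retrospective observational cohort study". The second primary objective is "To compare treatment strategies (endovascular, surgical, combined, or conservative management) and their angiographic and clinical outcomes". For that comparison, the Statistical Analysis Plan section of the protocol proposes "using appropriate statistical tests (e.g., chi-square, t-test, ANOVA, or non-parametric equivalents". It adds: "Multivariable regression models may be used to identify independent predictors of outcomes and recurrence". It mentions no center term, stratification, random effect or cluster-robust variance.

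Three other places bear on this:

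- Background and Rationale: "there remains significant variability in diagnostic timelines, treatment strategies (endovascular, surgical, or combined), and reported outcomes across institutions".
- Data Collection and Variables, under demographics and center information, lists "Study center (institution name" as a collected field, along with country.
- Study Design admits patients "evaluated and/or treated at their institution", and Data Collection and Variables states "All data will be fully de-identified prior to submission". No rule limits a patient to one record, and no check across centers is described.

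**The concern.** There are two separate problems.

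**Center.** Patients at one hospital share operators, equipment, referral patterns and scoring habits, so their outcomes may be correlated. If hospitals also differ in the modality they favor, a pooled test that ignores center goes wrong in two ways. It treats correlated records as independent, which can make p-values too small and intervals too narrow. It also lets differences between centers in skill, outcome scoring and case mix appear as differences between modalities. This second error is a bias, and more patients do not reduce it. Both bear on a primary objective.

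**Double entry.** A patient evaluated or first treated at one participating center and treated at another satisfies the entry rule at both. With de-identified submissions, the coordinating center cannot recognize the second record directly. Failure, recurrence and complication rates are then computed on a denominator that may count some patients twice.

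**Working it through.** The protocol gives no sample size, number of centers, center size, ICC or duplicate rate, so there is no figure of its own to reproduce. Every input below is an assumption chosen for illustration.

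**1. Clustering.** For a naive two-group comparison, let m be patients per center, ρy the outcome ICC, and ρx the correlation of modality within centers (1 if each center uses one modality, 0 if modality is unrelated to center, −1/(m−1) if it is exactly balanced in each center).

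- Variance inflation: D = 1 + (m − 1) × ρx × ρy
- True type I error of a nominal two-sided 5% test: 2 × [1 − Φ(1.96/√D)]

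With m = 20 and ρy = 0.05:

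| Modality within centers | D | √D | Type I error, formula | Type I error, simulated |
|---|---|---|---|---|
| Fixed by center, ρx = 1 | 1 + 19 × 1 × 0.05 = 1.95 | 1.396 | 0.160 | 0.148 |
| ρx = 0.6 | 1 + 19 × 0.6 × 0.05 = 1.57 | 1.253 | 0.118 | 0.105 |
| ρx = 0.1 | 1 + 19 × 0.1 × 0.05 = 1.095 | 1.046 | 0.061 | 0.059 |
| Balanced, ρx = −1/19 | 1 − 0.05 = 0.95 | 0.975 | 0.044 | 0.039 |

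The simulation ran t-tests on 20 centers of 20 patients, with 4,000 replicates per row. It agrees with the formula to within about 1.3 percentage points. √D is the factor by which the true standard error exceeds the reported one, so in the first row the reported value is 1/1.396 = 72% of the true one.

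Over m = 10 to 40 and ρy = 0.01 to 0.10:

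- ρx = 1: type I error 0.06 (D = 1.09) to 0.38 (D = 4.9)
- ρx = 0.3: 0.053 to 0.18
- ρx = 0: 0.05, no inflation
- balanced within centers: 0.039 to 0.049, slightly conservative

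The concentration of modality by center therefore decides whether there is a problem at all. These figures concern false positives from correlated records with no confounding; bias from center differences would come on top.

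**2. Duplicates, effect on a failure rate.** Assume 200 patients, of whom 15% (30) fail first treatment, with 30% of those failures (9) entered by a second center, giving 209 records.

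- Both centers record the failure: (30 + 9)/209 = 18.7%
- The second center records only its own success: 30/209 = 14.4%

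The true value is 15.0%, so the same double entry can push the rate either way.

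**3. Duplicates, effect on precision.** If a fraction q of patients is entered twice in the same modality group with the same outcome, the variance of the total is proportional to (1 − q) + 4q = 1 + 3q, while the naive analysis uses 1 + q. Hence D = (1 + 3q)/(1 + q). For q = 1%, 5% and 10%, D is 1.02, 1.10 and 1.18, and type I error is 0.052, 0.061 and 0.071. This is smaller than the effect of strong clustering.

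**The case against.** The best defense is that the protocol does not commit to the error. The tests are examples of what is appropriate, regression is permitted, center and country are recorded, and a separate analysis plan may specify the model. That stands to this extent: nothing says center will be ignored. But the protocol has its own analysis section, that section names methods for a primary objective, and every named method assumes independence. The regression is optional and is tied to finding predictors.

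A reader might infer three stronger claims that the documents do not support.

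- *Center largely determines modality.* The Background speaks only of variability across institutions in general. It says nothing specific about the participating centers, and variability is compatible with each of them using several modalities.
- *P-values will be too small.* This requires both an outcome ICC above zero and modality concentrated by center. With modality balanced within centers, the naive test is slightly conservative. The 16% figure belongs to the extreme case.
- *Double entry inflates failure rates.* Nothing in the protocol shows that failures are the cases most often referred on, and the arithmetic shows that the direction depends on what the second center records. The exclusion of cases without enough data on diagnosis or treatment would remove some records of patients who were only evaluated, and the Timeline schedules data cleaning. Neither would catch a patient treated and fully documented at two centers.

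**Conclusion.** The point holds in a conditional form. The named tests ignore a grouping that the protocol itself gives reason to think matters for both treatment and outcome, and a better method is available with a field already collected. How far the tests mislead depends on quantities the protocol does not give. At 20 patients per center and an ICC of 0.05, both assumed, the true error rate of a nominal 5% test lies between about 4% and 16%, according to how far modality is concentrated by center. Bias from center differences in skill, scoring and case mix is a further risk, and its size cannot be computed from the documents.

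Double entry is possible under the entry rule and no stated step guards against it. Its frequency and the direction of its effect are unknown. Neither problem invalidates the registry, and both can be corrected before the analysis.

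**What to change.** **Analysis.** Make the modality, diagnostic-delay and predictor comparisons with models that account for center: a center random intercept, or center-stratified or conditional models. Keep the simple tests as descriptive only. A random intercept deals with the correlation but removes center confounding only in part; adding each center's modality mix as a covariate separates the within-center effect from the between-center one. If cluster-robust variance is used and there are few centers, apply a small-sample correction.

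**One record per patient.** State that the center giving the first treatment enters the case, or the diagnosing center if the patient was managed conservatively. Before lock, screen across centers for likely duplicates on sex, age, fistula level, side and, where there is one, treatment year. Ask the contributing centers about matches where local approvals allow. Otherwise exclude suspected duplicates in a sensitivity analysis.

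**Cost.** The fields needed are already on the collection sheet. Intervals will widen where modality is concentrated by center, and centers that use a single modality add nothing to a conditional comparison. The duplicate check takes a modest number of center queries, and each center must still be able to trace its own study numbers. The entry rule is best issued before data collection closes at the end of February 2026.
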